8.3 Premature Patient Withdrawal

All patients will be advised that they are free to withdraw from participation in this study at any time, for any reason, and without prejudice. Every reasonable attempt should be made by the investigator to keep patients in the study; however, patients must be withdrawn from the study if they withdraw consent to participate. Investigators must attempt to contact patients who fail to attend scheduled visits by telephone or other means to exclude the possibility of an AE being the cause of withdrawal. Should this be the cause, the AE must be documented, reported, and followed as described in Section 11.2.

The sponsor reserves the right to request the withdrawal of a patient due to protocol violations or other reasons.

The investigator also has to withdraw patients from the study at any time for the following reasons:

- Unacceptable toxicity
- More than 3 weeks delay of scheduled infusion of CetuGEX™/cetuximab (i.e., missing more than 2 consecutive infusions)
- Intercurrent illness interfering with study procedures
- Noncompliance with study procedures, or
- Pregnancy.

If a patient is withdrawn from treatment prior to PD due to unacceptable toxicity or any other reasons as detailed above except noncompliance with study procedures, the patient will remain on regular study schedule until progression of disease unless this might interfere with the patient's best interest.

If a patient is withdrawn from the complete study before documented progressive disease, the reason for withdrawal and the date of discontinuation will be recorded on the appropriate electronic case report form (eCRF). Whenever possible, the evaluations that were to be conducted at the Final Examination should be performed at the time of premature discontinuation.

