9.12.2 Prohibited Therapies

The following co-medication/therapies are not allowed during participation in the study:

- EGFR targeting agents apart from randomly assigned study medication until end of treatment.
- Any other immunotherapy until end of treatment.
- Any anti-cancer treatment other than described in this protocol until end of treatment.
- Ongoing regular doses of hydrocortisone and steroids (except for topical/inhaled) other than corticosteroids used for precaution of IRR.
- Immunosuppressive agents until end of treatment.
- Radiation therapy (except palliation of existing bone metastasis pain).
- Erythropoietin (Epo).
- Other medications that are contraindications to 5-FU and cisplatin or carboplatin respectively as per SmPC 4.3 “Contraindications” and 4.5 “Interaction with other medicinal products and other forms of interaction” (see Appendices F, G, H).

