13.1 Study Endpoints

13.1.1 Primary Endpoint

Primary endpoint of the trial is PFS defined as time from randomization until disease progression or death of any cause. Date of disease progression is defined as the date of imaging showing disease progression, assessed by the investigator according to adapted immune-related RECIST 1.1 (modified irRC).

The PFS time will be censored at the time of the last tumor assessment if the patient is alive and without progression at the last time of observation.

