13.4.3 Efficacy Analyses

13.4.3.1 Primary Analysis

Primary endpoint of the trial is PFS defined as time from randomization until disease progression (assessed by the investigator) or death of any cause. The PFS time will be censored at the time of the last tumor assessment if the patient is alive and without progression at the last time of observation.

The primary efficacy analysis for PFS will be based on the ITT population. A log-rank test will be used to test the null hypothesis of equal treatment effects at an overall significance level of 0.05. The primary efficacy analysis will not be stratified by the

factors used for stratification at randomization in order to preserve the estimated power considering the high number of strata. As a sensitivity analysis, a proportional hazards regression model will be applied and the effects of the stratification factors, the p16 status, and the EGFR status will be estimated:

- FcγRIIIa status (FF or FV or VV),
- p16 status (+/-),
- EGFR status (+/-),
- Oral cavity and oropharynx vs. other locations,
- Locally recurrent vs. metastatic disease.
- EGFR treatment naïve vs. EGFR treatment as part of multimodal treatment.

The Kaplan-Meier method will be used to estimate the survival functions. Median survival times together with their 95%-confidence intervals will be retrieved from the survival functions.

The analysis will be repeated for the PP population as a sensitivity analysis.

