## **2.2 Efficacy and Safety Endpoints (Target Variables)**

### **2.2.1 Efficacy Variables**

#### Primary efficacy endpoint

The primary efficacy endpoint is PFS as assessed by the investigator.

PFS is defined as time from randomization until disease progression or death of any cause. Date of disease progression is defined as the date of imaging showing disease progression, as assessed by the investigator according to adapted immune-related RECIST 1.1 (modified irRC) [5]. The PFS time will be censored at the time of the last tumor assessment if the patient is alive and without progression at the last time of observation.

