Variable Name	Computation Methods, Notes, or Equation(s)		
PFSp  (primary definition)	= Earliest date of progression or death - date of randomization + 1 The earliest date of PD will be used irrespective of PD confirmation		
	Finding	Date of PD of Censoring	Outcome
	No PD or death	Pre and post-baseline imaging done: Date of last imaging	Censored
		No baseline or no post-baseline imaging done: Date of randomization	Censored
	Progression/death documented after a new anticancer treatment has started PD at scheduled visit PD between scheduled visits	Date of last imaging prior to new anticancer treatment Date of imaging Date of imaging	Censored Event Event
PFSs  (sensitivity definition)	= Earliest date of progression or death - date of randomization + 1 The earliest date of PD will be used irrespective of PD confirmation		
	Finding	Date of PD of Censoring	Outcome
	No PD or death	Pre and post-baseline imaging done: Date of last imaging	Censored
		No baseline or no post-baseline imaging done: Date of randomization	Censored
	Progression/death documented after a new anticancer treatment has started PD at scheduled visit PD between scheduled visits*	Date of last imaging prior to new anticancer treatment. Date of imaging Date of next scheduled visit	Censored Event Event
	PD after 2 or more missing scheduled visits	Date of last imaging prior to first missing visit.	Censored
	Death up to 16 weeks (112 days) after last imaging Death later than 16 weeks (112 days) after last imaging	Date of death Date of last imaging	Event Censored
Best overall response	Best modified irRC classification (CR, PR or SD) as assessed by the investigator or by the independent centralized review		

(rates) (BO(R))	SD: follow-up measurements must have met the SD criteria at least once after randomization at a minimum interval of 8 weeks.
Objective response (rate) (OR(R))	Best response of CR or PR
Clinical benefit (rate) (CB(R))	Best response of CR or PR or SD. SD: follow-up measurements must have met the SD criteria at least once after randomization at a minimum interval of 8 weeks

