### 9.1 Primary Efficacy Analysis

The primary efficacy analysis for PFS as assessed by the investigator will be based on the ITT population using the PFSp definition as described in Section 7.2.

A two-sided log-rank test will be used to test the null hypothesis of equal treatment effects at an overall significance level of 0.05. The Kaplan-Meier method will be used to estimate the survival functions. Median survival times together with their 95%-confidence intervals will be retrieved from the survival functions. PFS rates at 6, 12, 15 and 18 months and associated 95%-confidence intervals and graphs of the Kaplan-Meier curves by treatment arm will also be presented.

The primary efficacy analysis will not be stratified by the factors used for stratification at randomization in order to preserve the estimated power considering the high number of strata.

To investigate the influence of the stratification factor on the primary endpoint a Cox regression model will be applied as a sensitivity analysis based on the ITT population. This model will include the treatment effect and the stratification factors

- FcγRIIIa allotypes (FF, FV or VV)
- Oral cavity and oropharynx vs. other locations
- Locally recurrent vs. metastatic disease
- EGFR treatment naïve vs. EGFR treatment as part of multimodal treatment

The hazard ratios, the corresponding 95% confidence intervals and the p-values of the Wald test (using adjustment for ties according to Efron) will be presented for all factors. The Kaplan-Meier analyzes will be repeated separately within the subgroups formed by the stratification factors. Corresponding figures will combine the curves for all treatment group/factor level combinations on one page per factor. Factor levels maybe combined if the sample size per level is  $< 15$ .

Further sensitivity analyses will be done as follows

- The analyses will be repeated using the PFSs definition as described in Section 7.2
- The analyses will be repeated for the PP Population
- It has been recognized that not all sites had strictly applied modified irRC for response assessment. To investigate the influence of deviating response criteria on PFS a log rank test will performed stratifying sites according to strict adherence to modified irRC (yes/no).

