## **12. CHANGES COMPARED TO THE CLINICAL TRIAL PROTOCOL**

All planned statistical analyses are in agreement with the clinical trial protocol.

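### Both PFS definitions in the SAP censor events after new anticancer treatment; the protocol counts them, and the SAP declares no change

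*SAP*

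**What the plan says.** Protocol 13.4.3.1 has the primary endpoint "defined as time from randomization until disease progression (assessed by the investigator) or death of any cause". Protocol 13.1.1 gives one censoring condition: "The PFS time will be censored at the time of the last tumor assessment if the patient is alive and without progression" at the last observation. SAP Section 2.2.1 repeats both parts, beginning "PFS is defined as time from randomization until disease progression or death of any cause". None of these places mentions new anticancer treatment.

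SAP Section 7.2 then derives two variables, PFSp (primary) and PFSs (sensitivity). Each has a row for "Progression/death documented after a new anticancer treatment has started". In each, the outcome is censored and the date is the last imaging before the new treatment.

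SAP 9.1 bases the primary test on PFSp and adds "The analyses will be repeated using the PFSs definition as described in Section 7.2". SAP Section 12 states: "All planned statistical analyses are in agreement with the clinical trial protocol".

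**The concern.** A first progression or death that follows new therapy is an event under the protocol and under SAP 2.2.1, but it is censored under SAP 7.2. That reverses an outcome, so it is more than added detail, and it makes the SAP disagree with itself on its primary endpoint.

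Two things make it matter. First, the sensitivity definition carries the same row, so it cannot test whether this censoring is informative. Second, the trial is open label and the primary endpoint is assessed by the investigator, so a decision to change therapy before documented progression could depend on the arm. If it did, and if it anticipated progression, the hazard ratio would shift without any planned PFS analysis showing it. Meanwhile Section 12 tells the reader that nothing differs from the protocol.

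**Working it through.** **1. The same patient under each text.** A patient stops study treatment without progression, starts another anticancer drug between the week 12 and week 18 scans, and shows first progression at week 18.

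| Source | Outcome |
|---|---|
| Protocol 13.1.1, 13.4.3.1; SAP 2.2.1 | Event at week 18 |
| SAP 7.2, PFSp | Censored at week 12 |
| SAP 7.2, PFSs | Censored at week 12 |

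Progression documented before the new therapy remains an event everywhere. PFSs differs from PFSp only in unscheduled visits, missed visits and deaths more than 112 days after the last imaging.

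**2. Can such patients occur?** Yes. Protocol 9.12.2 prohibits "Any anti-cancer treatment other than described in this protocol until end of treatment", so the bar ends with study treatment. For patients withdrawn from treatment early for reasons other than noncompliance, Protocol 8.3 says "the patient will remain on regular study schedule until progression of disease unless this might interfere with" the patient's best interest. Later progressions are therefore generally imaged, and deaths are followed by phone.

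**3. Does any analysis recover the protocol endpoint?** No. The primary log-rank, Cox, per-protocol and irRC-adherence analyses (SAP 9.1), central reading (9.2.1), landmark (9.3.1), covariable models (9.3.2) and PK models (9.3.3) all rest on PFSp or PFSs.

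**4. The plan's own figure.** Inputs from Protocol 13.2: medians 5.6 and 8.4 months (HR = 5.6/8.4 = 0.667), two-sided alpha 0.05, power 80%, 1:1 allocation. By Schoenfeld, the events needed are 4(1.960 + 0.842)²/(ln 0.667)² = 191, against 192 stated. Power at 192 events is Φ(√192/2 × 0.4055 − 1.960) = 80.2%. The plan's figure is reproduced.

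**5. Loss of events (switching rates assumed).** Hazards are ln 2/5.6 and ln 2/8.4 per month, with 120 patients per arm, uniform 24-month accrual and a cut-off 12 or 18 months after the last randomization (the SAP Section 5 cap). The expected event fraction per arm is λ/(λ+η) times the mean of 1 − exp(−(λ+η)u), with u uniform from 12 to 36 months (18 to 42 at the cap). A drop-out hazard η of 0.0124 per month gives the planned 10% drop-out at 12 months. Hazards of 0.0195, 0.0275 and 0.0363 give 15%, 20% and 25%.

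| Further patients censored | Events at 12 months (power) | Events at 18 months (power) |
|---|---|---|
| 5% | 185 (79%) | 193 (80%) |
| 10% | 175 (77%) | 182 (78%) |
| 15% | 166 (74%) | 172 (76%) |

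With none, 194 events are expected at 12 months (power 81%).

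**6. Effect on the hazard ratio (simulation, assumed rates).** There were 12,000 trials per scenario with the same inputs, scans at weeks 6, 12 and 18 and every 8 weeks thereafter, and an unstratified log-rank test and Cox HR at 12 months. A given share of patients switches at a time uniform in the 6 weeks before the event and is censored at the last scan before the switch. Type I error is two-sided.

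| Share switching, control / CetuGEX | Result |
|---|---|
| none | 194 events, power 80% |
| 10% / 10% | type I error 5.2%; true HR 0.67 shows as 0.66; power 76% |
| 5% / 10% | true HR 1 shows as 0.96; type I error 6.3% |
| 10% / 5% | true HR 0.67 shows as 0.70; power 67% |
| 10% / 20% (stress case) | type I error 10.5% |
| 20% / 10% (stress case) | true HR 0.67 shows as 0.73; power 50% |
| 10% / 20%, unrelated to prognosis | true HR 0.67 stays 0.67; type I error 4.9% |

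At 5% / 8% the type I error (5.6%) cannot be told apart from nominal: an independent simulation gave 4.5% to 5.0%.

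**The case against.** Censoring at new therapy is a defensible convention. The protocol never mentions new therapy, and its Section 13 calls itself a summary and leaves detail to the SAP, so Section 7.2 could be read as that detail. The first part stands: which rule should be primary is open to debate. The second does not remove the problem, because the row narrows an event definition that covers death of any cause, conflicts with SAP 2.2.1 and is not declared.

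The affected group may be small. A patient must stop for a reason other than progression, remain progression-free and then start another therapy. Protocol 9.12.2 also lists radiotherapy separately, barred without an end-of-treatment limit except for palliation of pain from existing bone metastases, which narrows the group further. This stands and limits the likely size.

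Other analyses give partial checks. Duration of response in SAP 7.2 has no new-treatment censoring and has planned log-rank tables, but it covers responders only. TTF and OS are not PFS. The listings would hold patient-level data, but no by-arm table is planned.

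Finally, material bias needs switching that both differs by arm and falls shortly before the event. The 10%/20% and 20%/10% rows are stress cases with no basis in the documents. The simulation also dates progression at its underlying time; dating it at scans gives about 190 events rather than 194 before any switching. If the planned 10% drop-out already includes switchers, the loss of events is smaller or nil. All of this stands and is why no size is claimed for the actual trial.

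**Conclusion.** The concern holds. The contradiction is plain from the text and needs no assumption: as written, no planned analysis estimates the protocol's PFS, and the statement in SAP Section 12 is incorrect for the primary endpoint.

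The size and direction of any effect on the result are unknown, because the documents give no switching rate. Balanced switching, or switching unrelated to prognosis, costs some power and leaves the HR nearly unchanged. Modest imbalance that anticipates progression (5% against 10%) moves a true HR of 1 to about 0.96 and type I error to about 6%; in the reverse direction it lowers power to about 67%. Larger distortion needs larger imbalance. This should be fixed before database lock. It does not invalidate the design.

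**What to change.** Before database lock, give the primary endpoint one definition, in one of two ways.

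- **Option (a).** Remove the new-treatment row from PFSp, so that the primary analysis follows Protocol 13.1.1, and keep the row in PFSs.
- **Option (b).** Keep the row in PFSp. Add a named ITT sensitivity analysis (log-rank, Kaplan-Meier and Cox as in SAP 9.1) that counts progression and death regardless of new therapy. Align SAP 2.2.1 with 7.2, and list the change in Section 12.

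Under either option, tabulate by arm the number of patients whose first progression or death follows new therapy, so that readers can see whether switching differed.

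The cost is one derived variable, one small table and text edits to SAP 2.2.1, 7.2 and 12. No new data are needed: concomitant medication is recorded up to the Final Examination and anti-tumor therapy after progression is recorded thereafter. The drawback is that events after new therapy may dilute the contrast between the study drugs. PFSp has no missed-visit or 112-day limit, so some of the added events would be late deaths that reflect later treatment. PFSs has those limits and remains as the check.

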7 STUDY DESIGN

7.1 Overall Study Design and Plan

7.1.1 Overview

This is a phase II, randomized, controlled, multicenter study with first line treatment (6 cycles of 5-FU and cisplatin in combination with CetuGEX™ vs. combination with cetuximab) followed by single-agent maintenance therapy (CetuGEX™ or cetuximab, respectively).

The randomization to CetuGEX™ vs. cetuximab will be performed using a 1:1 ratio and will be stratified by:

- FcγRIIIa status (FF or FV or VV)
- Oral cavity and oropharynx vs. other locations

- Locally recurrent vs. metastatic disease
- EGFR treatment naïve vs. EGFR treatment as part of multimodal therapy.

The study will include 3 separate study periods following screening:

Combination treatment phase:

Eligible patients will be randomized to receive as first line treatment either CetuGEX™ or cetuximab in combination with chemotherapy (5-FU and cisplatin) for the maximum duration of 6 cycles of combined treatment. In case of toxicity, chemotherapy can be dose reduced, discontinued or, if later than the first cycle, switched to carboplatin. If discontinued earlier for any other reason apart from progression, patients will start the maintenance phase at that time.

As soon as at least 10 patients per treatment arm have completed the second cycle of combination therapy, patient safety data will be reviewed by an independent data safety monitoring board (DSMB).

Single-agent maintenance phase:

After completion or discontinuation of combination chemotherapy for any other reason apart from progression, the treatment will be followed by maintenance therapy with CetuGEX™ alone or cetuximab alone, respectively. Single-agent maintenance therapy will be continued until progression of disease or limiting toxicity.

Follow-up:

A Safety Visit must be performed 28 (+2) days after the last administration of the study drug for all randomized patients. In case of treatment discontinuation due to reasons other than disease progression, patients will stay on the regular study schedule until disease progression is documented and will then attend a Final Examination Visit. In case of treatment discontinuation due to disease progression, the Safety Visit is identical to the Final Examination Visit.

After the Final Examination, patients will be followed-up by quarterly phone calls until death or for a maximum duration of 24 months after randomization of the last patient for assessment of overall survival.

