10.1 Study Periods and Schedule of Visits

10.1.1 Screening Visit

The patient must be screened within 28 days prior the day of first infusion.

The following records and assessments will be performed at screening:

- Obtain written informed consent.
- Contact the IWRS to obtain patient identification number.
- Check of inclusion/exclusion criteria.
- Check availability of pre-existing tumor tissue sample for EGFR and p16 status assessment.
- Demographic information (including age, race, smoking status and alcohol consumption).
- Diagnosis of SCCHN, including oncological information, previous chemotherapy and radiotherapy and other oncological regimens.
- Medical history apart from SCCHN, including current therapies (e.g., prescription and non-prescription medication).
- Record ECOG performance status.
- Physical examination including underlying disease, weight, height and BMI.
- Vital signs (blood pressure, heart rate and body temperature).
- 12-lead ECG.
- Echocardiogram (ECHO)/Multiple Gated Acquisition (MUGA) scan for confirmation of eligibility (exclusion criterion 13).
- Evaluation of tumor size by computed tomography (CT) or magnetic resonance imaging (MRI) (head and neck region, chest, and abdomen).
- Blood and urine sampling for safety laboratory (hematology, coagulation panel, blood chemistry and urinalysis). Please note that creatinine clearance needs to be assessed at screening unless previous results not older than 6 weeks are available.

- Blood sampling for genotyping (FcγRIIIa status; only in case the patient will enter the study, the blood sample might also be used at a later time point for further analyses like FcγRII status).
- Recording of previous and concomitant medication.

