### **5. SAMPLE SIZE DETERMINATION**

Approximately 240 patients will be randomized in this study.

The log-rank test will be used to test the hypothesis that patients assigned to the CetuGEX™ arm have increased PFS compared to patients assigned to the control arm.

The sample size calculation is based on the following assumptions:

- The median PFS in the control arm is expected to be 5.6 months post randomization.
- It is expected that the median PFS in the CetuGEX™ arm can be increased to 8.4 months corresponding to a hazard ratio of 0.67.
- The overall trial duration will be approximately 36 months with an anticipated recruitment time of 24 months, anticipated treatment phase until PFS events are reached of approximately 12 months after randomization of the last patient (data

cut-off for main analysis) and ongoing follow-up for overall survival for at least 24 months after randomization of the last patient.

- Drop-outs are expected to occur at times following an exponential distribution and resulting in a drop-out rate of 10% at the cut-off for PFS analysis.
- Patients will be randomized in a 1:1 ratio.
- The overall two-sided significance level will be 0.05 and the power to be maintained 80%.

Based on these assumptions, approximately 240 patients have to be randomized to observe the required overall number of 192 events.

If the required number of events is not reached as planned after 12 months from last patient randomized, the main analysis will be postponed to obtain more events but not more than additional 6 months.

Assuming a corresponding effect on OS (hazard ratio 0.67) and a median overall survival of 10.6 months in the control group the number of survival events to be observed after a 24-months follow-up for survival will be 183.

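### SAP 7.2 cuts follow-up at new anticancer therapy only for patients who later fail, which lifts the late PFS estimates, and it lets some censoring dates fall before randomization

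*SAP*

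**What the plan says.** The primary analysis (SAP 9.1) is an unstratified log-rank test on investigator-assessed PFS in all randomized patients, using the PFSp table of SAP 7.2. The PFSs table is a sensitivity definition. Both compute time as event or censoring date minus randomization date plus 1.

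- **New-therapy row (both tables).** It applies when progression or death is documented after new anticancer treatment has begun. The patient is censored at "Date of last imaging prior to new anticancer treatment".
- **Row for patients with neither progression nor death (both tables).** With baseline and post-baseline scans, censoring is at the last imaging, with no limit at the start of new therapy. Otherwise: "No baseline or no post-baseline imaging done: Date of randomization". This fallback appears in no other row.
- **Extra PFSs rows.** Progression after two or more missed visits is censored at the last imaging before the first missed visit. The row "Death later than 16 weeks (112 days) after last imaging" is censored at the last imaging.

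On follow-up after stopping treatment for reasons other than progression, Protocol 7.1.1 says that "patients will stay on the regular study schedule until disease progression is documented". On baseline, Protocol 10.1.1 says: "The patient must be screened within 28 days prior the day of first infusion". The protocol's own PFS definition (13.1.1 and 13.4.3.1) censors only patients who are alive without progression. It has no new-therapy rule.

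**The concern.** Whether events after new therapy should count is a legitimate choice, and either answer can be applied to everyone. These tables mix the two. Time after the switch is kept for switchers who stay event-free and removed for switchers who fail. The risk set then contains people who, by construction, cannot have a counted event. The late hazard is diluted and the Kaplan-Meier curve sits too high, most of all at the 12-, 15- and 18-month rates that SAP 9.1 will report. If switching differs by arm, which is possible in an open-label trial, the hazard ratio moves as well.

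The second problem is one of dates. Where no post-baseline scan exists, the last imaging is the screening scan, taken before randomization. A zero or negative time enters no risk set, so the patient leaves the analysis or is repaired by an undocumented programming decision.

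**Working it through.** **Design figures first.** SAP 5 states "The median PFS in the control arm is expected to be 5.6 months post randomization" and, for CetuGEX, "can be increased to 8.4 months corresponding to a hazard ratio of 0.67". With 5.6/8.4 = 0.667, two-sided 0.05 and 80% power, Schoenfeld gives 4(1.960 + 0.842)²/(ln 0.667)² = 191 events against 192 stated. With 24 months of accrual, cut-off at 36 months and 10% of patients actually dropping out, 240 patients yield 194 events. The design reproduces, so its medians and timing are used below.

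**How the rule works.** Scans fall at weeks 6, 12, 18, 26, 34 and so on. Two patients start new therapy in week 20. One progresses on the week-34 scan and is censored at week 18. The other is still event-free at the week-74 scan and is censored at week 74. The second adds 56 event-free weeks after week 18; the first adds none.

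**Size, in closed form.** Let λ be the event hazard, θ the switching hazard, s = θ/(λ+θ) the share switching before an event, C the follow-up (uniform, 12–36 months) and f the fraction of switchers still scanned. Switching is independent of prognosis. Only unswitched patients can have a counted event, but event-free switchers stay in the denominator, so the counted hazard is λ/(1+r), where

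r(t) = f · (e^{θt} − 1) · mean of e^{−λ(C−t)} over C > t.

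Control arm, s = 20%, f = 1: λ = ln2/5.6 = 0.1238, θ = 0.25λ = 0.0309. At 18 months r = (e^{0.557} − 1) × (1 − 0.1078)/2.228 = 0.745 × 0.400 = 0.30, so the counted hazard is 0.77λ. At 12 and 6 months r is 0.14 and 0.03. Integrating λ/(1+r) to 18 months gives PFS of 13.0%, against 2^(−18/5.6) = 10.8%.

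A simulation on the SAP scan grid (400,000 patients per arm and scenario, progression dated at the next scan, all switchers scanned) agrees. Its true 18-month values can be checked by hand: the last scan is week 74 = 17.02 months, and 2^(−17.02/5.6) = 12.2%, 2^(−17.02/8.4) = 24.6%.

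18-month PFS under the SAP rule:

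| Assumed share switching | Control, closed form (true 10.8%) | CetuGEX, closed form (true 22.6%) | Control, scan grid (true 12.1–12.2%) | CetuGEX, scan grid (true 24.5–24.6%) |
|---|---|---|---|---|
| 5% | 11.2% | 23.2% | 12.7% | 25.1% |
| 10% | 11.7% | 23.8% | 13.3% | 25.9% |
| 20% | 13.0% | 25.4% | 14.7% | 27.4% |

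Censoring every switcher at the last scan before the switch gives 12.1–12.2% and 24.5–24.6% on the grid at these shares, so the excess comes from the mixture of rules. At 6 months the excess is 1 point or less. With f = 0.5, r halves: at 20% the control figure falls from 13.0% to 11.9%. With f = 0, r = 0. A variant with 15% of events as deaths and switching only before the underlying progression gives smaller control excesses: 0.3, 0.7 and 1.8 points.

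**Hazard ratio.** With equal switching, r is similar in both arms and the ratio moves by 0.002 or less. With no drug effect, all scans continuing and an assumed 25% switching on CetuGEX against 10% on control, the ratio at time t is (1 + r control)/(1 + r CetuGEX): 1.013/1.043 = 0.97 at 6 months and 1.057/1.205 = 0.88 at 12 months. Most events are early, and the overall simulated value is about 0.95. It is about 0.975 if half stop scanning. Reversing the arms gives about 1.06.

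**Dates.** With a scan 28 days before first infusion and randomization 1–3 days before it (Protocol 10.1.2), the scan precedes randomization by 25–27 days, so the derived time is −25 + 1 = −24 to −27 + 1 = −26 days. A scan 1 day before randomization gives 0.

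- **PFSp:** one route, namely new therapy before any post-baseline scan (first due at week 6), followed by progression or death. Expected patients per 120, control/CetuGEX: 1.0/0.6 at 5% switching, 2.1/1.2 at 10%, 4.6/2.8 at 20%.
- **PFSs only:** also progression after missing weeks 6 and 12, and death more than 112 days after a sole screening scan. With the earliest permitted scan, that means death after day 112 − 27 = 85 to 112 − 25 = 87.

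**The case against.** The best defence is that switchers may not be scanned after the switch. Protocol 8.3 waives the schedule where it conflicts with the patient's interest and excludes non-compliant patients from it. Complete withdrawal leads to a final examination without imaging and then phone calls (10.1.5). SAP 7.2 describes tumor assessment for the two treatment phases. If scanning always stops at the switch, the two rows give the same date. This stands as a limit on size. It does not remove the fault, because Protocol 7.1.1 and 8.3 make continued scanning the default and 9.12.2 bars other anticancer treatment only until end of treatment.

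It is also fair that every switching rate here is assumed, that the primary test is the log-rank, and that the 18-month rate is a descriptive tail estimate. SAP 7.2 allows further derivations to be described in the study report, which could cover a minimum date at randomization but not outcome-dependent censoring.

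Three stronger readings are tempting and not supported:

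- **That early failures generally leave the analysis.** Under PFSp, progression or death without prior new therapy still counts. The missed-visit and 112-day routes exist only in PFSs.
- **That the primary comparison is materially biased, or biased towards CetuGEX.** That needs a large difference in switching between arms together with continued scanning. The documents indicate neither its size nor its direction.
- **That a minimum date at randomization recovers the lost failures.** It makes the times valid, but patients censored at day 1 still add practically no information.

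**Conclusion.** Both derivation faults are present as written in PFSp and PFSs, and the outcome-dependent censoring is the one that matters. For an assumed 5–20% switching per arm, independent of prognosis, it inflates 18-month PFS by about 0.4 to 3 points with all switchers scanned (somewhat less in the variant above), by about half or less if half stop, and by nothing if all stop. The hazard ratio is affected only if switching differs by arm. The date fault concerns few patients and is mainly one of validity and of keeping all randomized patients in the analysis set. This should be fixed before database lock. It is not evidence that the primary test is unsound.

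**What to change.** In SAP 7.2, for both tables:

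1. **Main change.** In any analysis that keeps new-therapy censoring, censor every patient who starts new anticancer treatment before progression at the last imaging before it, whether or not an event follows.
2. **Dates.** No censoring date may be earlier than randomization. With no post-baseline scan, the 112 days run from randomization.
3. **Companion analysis.** Consistent censoring is itself informative if switching follows clinical worsening. So also report PFS with all progressions and deaths counted, as Protocol 13.1.1 and 13.4.3.1 define it. SAP 12 declares full agreement with the protocol and should record the new-therapy rule as a departure.

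The cost is a few sentences, a change to the derivation program and one more set of PFS outputs. No new data are needed.
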